1.4. Summary of the Known and Potential Risks and Benefits of Voxelotor

Clinical data to date have shown that treatment with voxelotor results in a dose-dependent increase in Hb within 2 weeks that is maintained through 24 weeks, and with an associated decrease in clinical measures of hemolysis (including indirect bilirubin, reticulocytes, and LDH), which correlates with drug exposure (Brown, 2018; Vichinsky, 2018). Durability of response is sustained through 72 weeks of treatment (Howard, 2021). By stabilizing HbS in the oxy-Hb state, voxelotor delays in vitro HbS polymerization and prevents RBC sickling in blood from patients with SCD (Oksenberg, 2016). By inhibiting HbS polymerization, voxelotor has been shown to improve RBCs deformability and reduce blood viscosity. Treatment with voxelotor has also led to significant reductions in sickle cell counts in the peripheral blood (Dufu, 2018), which support the potential for voxelotor to serve as a disease-modifying therapy for SCD.

Based on available data, voxelotor has been well tolerated over a range of tested doses up to and including 1500 mg daily in adult and pediatric clinical study participants with SCD (Studies GBT440-031, GBT440-001, and GBT440-007). There have been no concerning safety findings arising from review of data from the completed Phase 3 Study GBT440-031 and the ongoing Phase 2 pediatric study, GBT440-007.

Based on the safety data from the Phase 3 study in adult and adolescent participants with SCD, non-SCD-related treatment-emergent adverse events (TEAEs) were predominantly of low-grade severity and were transient. Identified risks include the adverse drug reactions (ADRs) of diarrhea, abdominal pain, nausea, rash, and drug hypersensitivity. As expected, SCD-related TEAEs were common, and the incidence of SCD-related TEAEs, including sickle cell anemia (SCA) with crisis, was similar for the voxelotor and placebo treatment groups. The profile of non-SCD-related and SCD-related TEAEs in adolescent participants was similar to the voxelotor treatment groups in the adult population.

Across all SCD studies, the overall incidence of TEAEs leading to study treatment discontinuation was low and the most commonly reported serious adverse events (SAEs) were predominantly assessed as not related to study treatment but to underlying SCD; predominantly SCA with crisis.

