Enrolled participants with TCD flow velocity value of \geq 220 cm/sec will have study drug discontinued and return for the EOS visit (28 days after the last dose of study drug). Patients will be treated according to local standard of care for abnormal TCD flow velocity.

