9. PROTOCOL DEVIATIONS31

10. CHANGES IN THE PLANNED ANALYSES31

11. REFERENCES32

12. TABLES, FIGURES, AND LISTINGS33

LIST OF TABLES

Table 1: Nominal Analysis Visit Windows18

090177e1a2bf4d41Approved\Approved On: 31-Jan-2025 17:16 (GMT)

Table 2: Date of Abnormal TCD Event or Censoring.....24

LIST OF FIGURES

Figure 1: Study Schema.....10

090177e1a2bf4d41\Approved\Approved On: 31-Jan-2025 17:16 (GMT)

SUMMARY OF SAP CHANGES

Version	Version Date	Summary of Changes
1.0	20 May 2023	N/A (original document)
2.0	11 Jan 2024	
 - Section 6.3 (Analysis Timing): Updated timing of the primary study analysis to be performed after all subjects have completed the study through Week 48 - Section 6.4.2.1 (TCD Change from Baseline): For subjects that discontinued early due to abnormal TCD, changed imputation method from last observation carried forward to multiple imputation - Section 6.4.2.3 (TCD Responder): Updated missing data rule such that all subjects with a missing TCD flow velocity at the assessment timepoint will be classified as non-responders. - Section 6.4.2.4 (Hemoglobin and Hemolysis Change from Baseline): Added a sensitivity analysis for change from baseline in hemoglobin. - Sections 6.4.3.2 (Stop Dates for Concomitant Medications) and 6.4.3.4 (Stop Dates for Adverse Events): Removed sections as not applicable - Section 8.2.1 (Primary Endpoint): Added multiple imputation - Section 8.2.2.2 (Time to Event Endpoints): Added censoring rule for two or more consecutively missed TCD assessment to Table 2 - Section 8.2.2.3 (TCD Response Endpoint): Added clarification on CI method; Updated missing data rule such that all subjects with a missing TCD flow velocity at the assessment timepoint will be classified as non-responders; Changed Week 24 assessment based on average of Week 24 and Week 28 to be a sensitivity analysis - Section 8.2.6 (Adjustment for Multiple Comparisons): Updated the order of testing for secondary endpoints - Section 8.2.8 (Sensitivity Analysis): Added worst observation carried forward and tipping point analyses as sensitivity - Minor edits for clarity and consistency

090177e1a2bf4d41\Approved\Approved On: 31-Jan-2025 17:16 (GMT)

Version	Version Date	Summary of Changes

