6.4.2.4. Hemoglobin and Hemolysis Change from Baseline

- For the primary method of analysis of these endpoints (MMRM), missing at random (MAR) will be assumed.
 - For change from baseline in Hb, a sensitivity analysis using last observation carried forward (LOCF) for subjects that discontinue the study early due to conversion to abnormal TCD flow velocity will also be performed.
- Subjects initiating HU postbaseline are to be discontinued from the study. Assessments of Hb and clinical measures of hemolysis obtained after HU initiation will be excluded from analysis.
- RBC transfusions: all laboratory results within 8 weeks after the transfusion date will be imputed for the MMRM change from baseline analysis of Hb and hemolysis measures. Post transfusion results will be imputed by data from the most recent Study

090177e1a2bf4d41Approved\Approved On: 31-Jan-2025 17:16 (GMT)

Visit prior to the transfusion (including Baseline) with a non-missing laboratory value.

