8.2.8. Sensitivity Analyses

The following sensitivity analyses will be performed to evaluate the robustness of the primary efficacy endpoint results to missing data assumptions:

- WOCF: For subjects discontinued early from the study due to conversion to abnormal TCD flow velocity, missing TCD values post abnormal TCD assessment will be imputed using WOCF. All other data handling rules in Section 6.4.2.1 and the MMRM model as described in Section 8.2.1 will be applied.
- Tipping point: A tipping point analysis will be conducted by adding (or subtracting) a constant delta (or so-called shift parameter) to the post-discontinuation imputed TCD values for subjects that discontinue early due to conversion to abnormal TCD flow velocity. A separate delta will be applied to each treatment group (voxelotor and placebo) in the direction of lack of efficacy (TCD flow velocity increase for voxelotor group and TCD flow velocity decrease for the placebo group). A range of values will be used to adjust the imputed TCD flow velocity values independently for each treatment group based on a grid of delta adjustments. The resulting point estimate for the treatment effect and corresponding p-value under each pair of deltas will be tabulated. If the delta parameter needed to overturn the conclusion is so extreme that it is considered clinically implausible, then this indicates robustness to missing data assumptions.

In addition, as study drug dosing was paused prior to study termination, the following sensitivity analysis will also be performed:

- Exclusion of TCD data post dose pause: For subjects ongoing in the study at the time of the dose pause, TCD data collected after their last dose of study drug will be excluded from analysis and change from baseline in TCD assessed based on the MMRM model as described in Section 8.2.1.

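### The labelled sensitivity analysis for hemoglobin change does not test loss of a voxelotor gain after drug is stopped for abnormal TCD, when the value carried forward was measured on drug

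*SAP*

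**What the plan says.** SAP 6.4.2.4 sets the missing-data rules for Hb. On the main model it states: "For the primary method of analysis of these endpoints (MMRM), missing at random (MAR) will be assumed". For change in Hb it then adds "a sensitivity analysis using last observation carried forward (LOCF) for subjects that discontinue the study early due to conversion to abnormal TCD flow velocity". The Summary of SAP Changes dates the addition to Version 2.0 ("Added a sensitivity analysis for change from baseline in hemoglobin"). That log is cited for history only; the operative rule is in 6.4.2.4.

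Two further rules in 6.4.2.4 decide which Hb values can be carried:
- On hydroxyurea (HU): "Assessments of Hb and clinical measures of hemolysis obtained after HU initiation will be excluded from analysis".
- Hb in the 8 weeks after a red-cell transfusion is replaced by the value from the study visit before it.

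Protocol 3.1.1 stops study drug after a confirmed abnormal TCD, and a child at or above 220 cm/sec "will have study drug discontinued and return for the EOS visit". The end-of-study (EOS) visit falls 28 days after the last dose, and care then follows the local standard. Protocol 1.4 reports that "treatment with voxelotor results in a dose-dependent increase in Hb within 2 weeks that is maintained through 24 weeks", and Protocol 1.6.1 cites exposure-response analyses for Hb.

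For TCD, SAP 8.2.8 says that "sensitivity analyses will be performed to evaluate the robustness of the primary efficacy endpoint results to missing data assumptions", using worst-value carry-forward and a tipping-point grid. It adds a check that drops TCD data after the dose pause. Section 8.2.8 has no counterpart for Hb.

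**The concern.** A sensitivity analysis should vary an assumption that the main analysis cannot verify. For a child taken off drug at conversion, that assumption is what Hb does afterwards. If every usable Hb for that child was measured on drug, the missing-at-random model extrapolates an on-drug course and LOCF freezes an on-drug value. Neither lets a drug-related gain fade. A placebo converter has no such gain to keep, so any error favours voxelotor.

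The two analyses could therefore agree and be reported as robust without the most plausible departure having been examined. LOCF also enters the filled value as if observed, so it adds no imputation uncertainty. The same SAP version "changed imputation method from last observation carried forward to multiple imputation" for TCD in these same children, which makes the choice for Hb stand out.

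At stake is the reading of a secondary endpoint, Hb change at Weeks 24, 48 and 96, not the primary result.

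**Working it through.** **Inputs from the SAP (6.1).** Placebo conversion 35% by Week 96; hazard ratio 0.5; 112 per arm; 20% dropout; 49 expected events; about 65% power at two-sided 5%.

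**Assumptions not in the documents.** Constant hazard; no mean Hb change on placebo; a gain of 1 g/dL in voxelotor children who do not convert; a gain d in those who do, with d from 0 to 1.5 g/dL. The value 1 g/dL is only a convenient reference, being the Hb-response cut in SAP 8.2.3.

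**Step 1: reproduce the plan's figure.**
- Voxelotor conversion by Week 96 = 1 − 0.65^0.5 = 19.4%.
- Events = 112 × 0.8 × (0.35 + 0.194) = 48.7, against 49 stated.
- Log-rank power by Freedman's formula = Φ(√49 × 0.5/1.5 − 1.96) = 64.6%, against about 65% stated.

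The conversion assumptions are therefore read as the plan intended.

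**Step 2: how many children the rule can touch.** Voxelotor share converted by week t: p(t) = 1 − 0.65^(t/192).

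| Week | p(t) | of 112 | after 20% dropout (of 89.6) |
|---|---|---|---|
| 24 | 5.2% | 5.9 | 4.7 |
| 48 | 10.2% | 11.4 | 9.1 |
| 96 | 19.4% | 21.7 | 17.4 |

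**Step 3: gain kept by LOCF.** If converters' on-drug gain d is lost after stopping, LOCF of an on-drug value overstates the voxelotor mean by p(t) × d.

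| Week | d = 0.5 | d = 1.0 | d = 1.5 |
|---|---|---|---|
| 24 | 0.03 | 0.05 | 0.08 |
| 48 | 0.05 | 0.10 | 0.15 |
| 96 | 0.10 | 0.19 | 0.29 |

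(g/dL; zero when d = 0.)

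**Step 4: what each analysis would show.** The LOCF difference is (1 − p) × 1 + p × d. Return to baseline gives (1 − p) × 1.

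| Converters' gain d | LOCF at Weeks 24 / 48 / 96 | Return to baseline |
|---|---|---|
| 1.0 | 1.00 / 1.00 / 1.00 | 0.95 / 0.90 / 0.81 |
| 0.5 | 0.97 / 0.95 / 0.90 | 0.95 / 0.90 / 0.81 |
| 0 | 0.95 / 0.90 / 0.81 | 0.95 / 0.90 / 0.81 |

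With d = 1.0 the missing-at-random model also gives 1.00 at each visit. It then agrees exactly with LOCF, while the gain has in fact been lost in converters. LOCF responds to a poor gain on drug, but not to a gain lost after stopping.

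**Step 5: why these sizes are ceilings at the planned rates.** A child found abnormal at the Week 24, 48 or 96 visit may have Hb observed at that visit, so fewer than p(t) have missing Hb. Some children may also have a usable off-drug Hb.

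**The case against.** The strongest reply is that the last Hb may not be an on-drug value. Protocol 3.1.1 and 3.4.2.2 call for an EOS visit 28 days after the last dose. SAP 6.4.1 assigns data to windows by study day, with contiguous windows from Day 2 to Day 714 and none reserved for EOS. SAP 8.2 includes data collected off drug. If Hb is drawn at EOS and remains usable, LOCF carries an off-drug value and the MMRM conditions on it too. This stands. A reader might infer that the check can never show loss of effect; the documents do not support that. The hematology row of Protocol Appendix B is not readable in the text used here, so whether Hb is drawn at EOS needs checking.

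The reply is not complete. Protocol 1.1 names transfusion and HU as the treatments that lower stroke risk in abnormal TCD. If either starts before EOS, 6.4.2.4 replaces or excludes that Hb, and the carried value reverts to an earlier one. How often this happens is not stated.

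Three other stronger readings also fail:
- **That nothing else in the plan guards the Hb result.** SAP 8.2.3 counts a child as an Hb non-responder at Week 24 if Hb is missing at both Weeks 24 and 28. That analysis is not labelled a sensitivity analysis and does not reach mean change or later visits. Some efficacy text is redacted and cannot be judged.
- **That SAP 8.2 makes the off-drug Hb the required target.** It concerns data from children who continue assessments, and 6.4.2.4 itself removes post-HU values and replaces post-transfusion values. Wanting the loss of effect examined is a reasonable choice of estimand, not one the SAP dictates.
- **That LOCF is uninformative.** It uses each child's own last value and moves when converters did poorly on drug.

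**Conclusion.** The point holds as an improvement to a sensitivity analysis. Among the analyses labelled as such, LOCF is the only one for Hb change. Where the last usable Hb is an on-drug value, neither it nor the main MMRM allows for loss of the gain after stopping, so their agreement is not evidence of robustness to that loss.

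The size is modest. The Step 3 values for a 1 g/dL gain apply if every converter's Hb is missing, the carried value is on drug and the gain is wholly lost. By Week 96 this concerns about 17 voxelotor children after planned dropout.

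A reader might take the Week 96 value as a threat to a trial conclusion. The documents do not support that: Hb is not in the test sequence in SAP 8.2.6, and SAP 6.3 makes Week 96 exploratory after early termination.

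**What to change.** Keep the missing-at-random MMRM as the main Hb analysis. In SAP 6.4.2.4, replace or supplement LOCF with multiple imputation of Hb after discontinuation for abnormal TCD, drawn from the placebo arm given the child's baseline and earlier Hb, and combined by Rubin's rules. This is preferable to carrying baseline forward, which shares LOCF's fault of treating a single filled value as observed. If LOCF is kept, state that a usable off-drug EOS Hb is the value carried.

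SAP 6.3 records the Week 48 analysis as already performed, with the final analysis to follow. A check added now should be labelled as added after the Week 48 analysis. If the SAP is not amended again, it can be reported under Section 10 as an additional analysis.

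The cost is a short text change and a new imputation program. The TCD code in SAP 8.2.1 resamples values of 200 cm/sec or more and is not a placebo-reference model, so only the combining step carries over. The Hb sensitivity estimate may also be less favourable to voxelotor.

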1. GLOSSARY OF ABBREVIATIONS

AE	adverse event
ALK	alkaline phosphatase
ALT	alanine aminotransferase
AST	aspartate aminotransferase
BTCD	baseline transcranial doppler

CCI

CMH	Cochran-Mantel-Haenszel
CRF	case report form
CTCAE	Common Terminology Criteria for Adverse Events
CV	coefficient of variation
DSMB	Data Safety Monitoring Board

CCI

EOS	End of Study
EOT	End of Treatment
GBT	Global Blood Therapeutics
Hb	hemoglobin
HbF	hemoglobin fetal
HU	hydroxyurea
ITT	intent to treat
IXRS	interactive response system
LDH	lactate dehydrogenase
LOCF	last observation carried forward
MAR	missing at random
MedDRA	Medical Dictionary for Regulatory Activities
mg	milligram
MI	multiple imputation
MMRM	mixed model for repeated measures

CCI

PK	pharmacokinetic(s)
PPK	population pharmacokinetic(s)
RBC	red blood cell
SAE	serious adverse event

090177e1a2bf4d41\Approved\Approved On: 31-Jan-2025 17:16 (GMT)

SAP	statistical analysis plan
SCD	sickle cell disease
SD	standard deviation
SOC	System Organ Class
TAMMV	time-averaged mean of the maximum velocity
TCD	transcranial doppler
TEAE	treatment-emergent adverse event
TIA	transient ischemic attack
VOC	vaso-occlusive crisis
WHO	World Health Organization
WOCF	worst observed value carried forward

090177e1a2bf4d41\Approved\Approved On: 31-Jan-2025 17:16 (GMT)

2. INTRODUCTION

The purpose of Study GBT440-032 (C5341021) is to evaluate the effect of voxelotor on reducing the risk of stroke, as measured by transcranial doppler (TCD) flow velocity in subjects 2 to < 15 years of age with sickle cell disease (SCD) who have conditional TCD flow velocity at baseline.

This document describes the statistical methods to be used in the summary and analysis of data from Study GBT440-032. Population pharmacokinetic (PK) analyses will be described in a separate document. Descriptive statistics for **CCI** may be summarized in a separate report. Where this document differs from the study protocol, the methodology described in the SAP is considered the latest and supersedes the corresponding section(s) in the protocol.

As of 1 May 2024, study drug dosing in GBT440-032 was voluntarily paused by the Sponsor due to a safety imbalance. Study visits and other study activities continued in accordance with the protocol. Subsequently, a decision was made by the Sponsor on 25 September 2024 to terminate the study based on the totality of clinical data for Oxybryta (voxelotor) and the last subject last visit occurred subsequently.

[figure not shown]
2.1. Study Overview

GBT440-032 is a multicenter, randomized, placebo-controlled, double-blind, prospective study evaluating the efficacy and safety of voxelotor in pediatric subjects with SCD, 2 to < 15 years of age. Approximately 224 subjects will be randomized 1:1 to voxelotor or placebo. The study schema is presented in Figure 1.

The duration of study involvement for an individual subject is expected to be approximately 105 weeks.

Subjects ≥ 12 years old will be administered a fixed dose of voxelotor 1500 mg per day. Subjects younger than 12 years of age will receive voxelotor at a weight-based (1500-mg equivalent) dose, as described in Section 1.6 of the protocol.

Figure 1: Study Schema

Abbreviations: EOT, end of treatment.

Note: Primary endpoint will be assessed at Week 24.

090177e1a2bf4d41Approved\Approved On: 31-Jan-2025 17:16 (GMT)

At least 15 subjects from 2 years to < 4 years of age will be enrolled. Administration of voxelotor will be initiated in subjects < 4 years of age after the Data Safety Monitoring Board (DSMB) has reviewed safety and PK data from at least 12 subjects < 30 kg treated with voxelotor for at least 28 days. The data for at least 12 subjects may be generated from any of the voxelotor studies.

Following completion of study treatment, eligible subjects will be given the option to enroll in an open-label extension study (under a separate protocol) to receive voxelotor for a minimum of 3 years (3 years or until commercial product or a managed access program becomes available, whichever is longer).

2.2. Study Measurements and Visit Schedule

Please refer to the study protocol amendment 4, Appendix A, Appendix B, and Appendix C for schedule of assessments.

3. STUDY OBJECTIVES

Primary Objective:

[figure not shown]
The primary objective is to evaluate the effect of voxelotor compared to placebo on the TCD time-averaged mean of the maximum velocity (TAMMV) arterial cerebral blood flow at 24 weeks in SCD subjects ≥ 2 to < 15 years of age with conditional (170 to < 200 cm/sec) TCD flow velocity.

Secondary Objectives:

[figure not shown]
The secondary objectives are to evaluate the effects of voxelotor compared to placebo on:

- Change in TCD flow velocity at Week 48 and Week 96
- Conversion of TCD category from conditional to abnormal
- Reversion of TCD category from conditional to normal
- Proportion of subjects with TCD response
- Change in Hb over time
- Change in clinical measures of hemolysis
- Annualized incidence rate of vaso-occlusive crises (VOCs)

CCI

CCI

Safety Objective:

The safety objective is to assess the safety and tolerability of voxelotor compared to placebo.

Pharmacokinetic Objective:

The pharmacokinetic objective is to assess the PK of voxelotor as evaluated by population PK (PPK) analysis.

4. STUDY ENDPOINTS

4.1. Primary Endpoint

[figure not shown]
The primary efficacy endpoint is the change from Baseline at 24 weeks in TAMMV arterial cerebral blood flow, as measured by TCD.

4.2. Secondary Endpoints

[figure not shown]
The secondary endpoints are:

- Change from Baseline in TCD flow velocity at Week 48 and Week 96
- Time to conversion to abnormal TCD flow velocity (≥ 200 cm/sec)
- Time to reversion to normal TCD flow velocity (< 170 cm/sec)
- Proportion of subjects with TCD flow velocity reduction ≥ 15 cm/sec at Week 24, Week 48, and Week 96
- Change in Hb from Baseline at Week 24, Week 48, and Week 96
- Change in clinical measures of hemolysis (unconjugated bilirubin, % reticulocyte, absolute reticulocyte, and lactate dehydrogenase [LDH]) from Baseline at Week 24, Week 48, and Week 96
- Annualized incidence rate of reported VOCs

CCI

090177e1a2bf4d41\Approved\Approved On: 31-Jan-2025 17:16 (GMT)

4.4. Safety Endpoints

The safety endpoints include adverse events (AEs), clinical laboratory assessments, and vital signs.

4.5. Pharmacokinetic Endpoints

The endpoint is whole blood and plasma voxelotor PK as evaluated by PPK analysis using nonlinear mixed effects modeling.

5. DEFINITIONS AND TERMINOLOGY

Study Treatment

The term study treatment refers to either voxelotor or placebo.

Baseline Value

Baseline measurements for efficacy and safety assessments will be the average of all pre-randomization or pre-first dose values, respectively, collected on or after Study Day -35 (see Table 1) with the exception of TCD flow velocity. For TCD flow velocity, the baseline value will be the value at Screening.

Day 1

Day 1 is the date of randomization.

Study Day

Study Day is defined relative to the date of randomization.

For study assessments or events that occur on or after the date of randomization, the study day of an assessment/event is calculated as:

$$\text{Study Day} = \text{Event date} - \text{Date of randomization} + 1.$$

For pre-randomization events, the study day is calculated as:

$$\text{Study Day} = \text{Event date} - \text{Date of randomization}.$$

Study Visit

Study Visit is the visit as defined in Table 1.

Treatment Day

Treatment Day is defined relative to the date of first dose.

Treatment day of an event that occurs on or after date of first dose is calculated as:

$$\text{Treatment Day} = \text{Event date} - \text{Date of first dose} + 1.$$

Treatment day of an event that occurs before date of first dose is calculated as:

$$\text{Treatment Day} = \text{Event date} - \text{Date of first dose}.$$

Exposure to Study Drug

Duration of exposure is defined as the number of weeks from date of first dose to date of last dose and is calculated as:

$$\frac{(\text{Date of last dose} - \text{Date of first dose} + 1)}{7}$$

Actual exposure is defined as the number of weeks from date of first dose to date of last dose excluding days where treatment was entirely missed or intermittently stopped as recorded in the case report form (CRF) and is calculated as:

$$\frac{(\text{Date of last dose} - \text{Date of first dose} - \text{Number of days study drug was not taken} + 1)}{7}$$

Completion of Treatment

[figure not shown]
Completion of study treatment is as specified on the End of Treatment (EOT) CRF and includes all subjects who did not permanently discontinue study drug early (ie, prior to the end of the 96-week treatment period).

Completion of Study

Completion of study is as specified on the End of Study (EOS) CRF. Subjects are considered to have completed the study if (1) the subject completed the study through the Week 96 visit and elected to enroll in the open-label extension study, or (2) the subject did not enroll in the open-label extension study and completed the study through 96 weeks plus the EOS follow-up visit (28 days after the last dose of study drug).

[figure not shown]
Change from Baseline

Change from baseline for a given endpoint is defined as the Study Visit value minus the Baseline value.

090177e1a2bf4d41\Approved\Approved On: 31-Jan-2025 17:16 (GMT)

CCI

Treatment-emergent Adverse Event

A treatment-emergent adverse event (TEAE) is defined as an adverse event (AE) with an onset date between date of first dose and 28 days after last dose, inclusive.

090177e1a2bf4d41\Approved\Approved On: 31-Jan-2025 17:16 (GMT)

Concomitant Medications

Concomitant medications are those medications taken on or after the initiation of study drug. This definition includes medications started prior to the initiation of study drug but continue concurrently with study drug.

Prior Medications

Prior medications are those medications taken prior to date of first dose.

